### Follow-up period:

Treatment by IPH2201 will be limited to 56 weeks, or less, in the event that a complete response with undetectable MRD is documented for 2 months.

[figure not shown]
Treatment by ibrutinib will be at least administered until the end of the study follow-up period (up to 12 months after end of IPH2201 treatment), unless disease progression (International Workshop on Chronic Lymphocytic Leukemia (IWCLL)), untoward toxicity, or consent withdrawal leads to the premature interruption of the ibrutinib treatment.

Patients will be enrolled for a post study follow-up enabling the investigator to document disease progression (IWCLL) or death, for 3 additional years after the completion of their in study follow-up.

Release date: 12 August 2016
Edition number

GED version MOD-3783

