#### Part 2: phase IIa

In the part 2, phase IIa of the clinical trial, the doses of IPH2201 will be selected by the safety committee.

In case of any grade ≥3 adverse event:

- o Treatment will be temporarily suspended for 2 weeks
- Treatment will be resumed at the same dosage in case of resolution to a grade 2 or lower
- In the absence of resolution to a grade 2 or lower, the treatment suspension will be prolonged by 2 more weeks
- In the absence of resolution to a grade 2 or lower after a 4-week suspension, the patient will be taken off study
- In case of recurrence of a grade 3 related reaction after a temporary suspension, the same suspension will apply, but after resolution to a grade 2 or lower, treatment will be resumed at the lower dose level

In case of IPH2201 treatment discontinuation, the continuation of ibrutinib treatment is left to investigator's discretion.

Release date: Edition number

GED version

12 August 2016 MOD-3783

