### 4.3 WITHDRAWAL CRITERIA

Patients will be withdrawn from the study in the following situations:

- Disease progression (IWCLL 2008 criteria)
- o Adverse events: a patient may be removed from the study following a severe (grade 3) or life-threatening (grade 4) adverse event at the discretion of the treating physician
- Withdrawal of consent by the patient
- Major protocol deviations (i.e., non-compliance with treatment procedures)
- Investigator's decision
- Sponsor's decision if an inacceptable toxicity observed in another patient led the Safety Committee to recommend a transient or permanent discontinuation of the study

After treatment withdrawal, patients will be followed for at least 4 weeks after last study drug administration or until recovery from all related adverse events to grade 1 or less, or until the toxicity level is stable for at least 6 weeks (except in case of consent withdrawal - see below). The patient will then complete the End of Study (EOS) visit.

After the EOS visit, information on the survival of the patients will be collected periodically by the sponsor through contact with the investigator. In addition, appropriate alternative treatment will be proposed by the investigator to the withdrawn patient.

CONFIDENTIAL

Release date: Edition number

GED version

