## 5.3.2 Not Permitted

The following concomitant treatments are not permitted until the end of the treatment period (End of Treatment) and must be stopped before the start of treatment accordingly with their pharmacological effects:

- o Any chemotherapy or other systemic anti-tumor therapy (including other monoclonal antibody)
- Any irradiation
- o Corticosteroids IV or *per os* (PO) (except for the treatment of grade ≥ 3 infusion reaction)
- Other Investigational drugs
- o Cytokines and/or growth factors
- Immunosuppressive agents
- o Antivitamin K anticoagulants

Strong CYP3A inhibitors (see appendix V) are contra-indicated if they must be given more than 7 days. If a strong CYP3A inhibitor must be given for 7 days or less consider interrupting ibrutinib until the CYP3A inhibitor is no longer needed.-If a moderate inhibitor (see appendix V) must be given for any time period, the dose of ibrutinib should be reduced to 140 mg. Strong CYP3A inducers (see appendix V) should be avoided with ibrutinib.

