### Phase IIa:

For the patients included in the phase IIa part of the study, follow-up visits are performed after the End of Treatment visit every 3 months for a 12-month period.

At follow-up visits the following assessments are required:

- Concomitant illness/Concomitant medication
- Tumor assessment:
  - o a tumor assessment by physical examination is required at all follow-up visits

Release date: Edition number

MOD-3783

12 August 2016

GED version

- a CT-scan should be performed to confirm a CR or progression, whenever one of these events is suspected
- Safety assessments:
  - Vital signs (including weight)
  - o Physical examination, focused on symptoms and new findings (from screening visit)
  - ECOG status
  - o Adverse events
- Safety laboratory
  - o Hematology
  - Biochemistry: at FU3, FU5, FU6, FU7 in phase lb, and at FU1, FU2, FU3 and FU4 in phase II (assessments every 3 months)
- PK/PD assessments

  o Pharmacokinetics

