3.2.3 Both phases

In both phases, treatment by monalizumab will be limited to 56 weeks, or less, in the event that a complete response with undetectable MRD is documented for 2 months. Treatment by ibrutinib will be at least administered until the end of the study follow-up period (up to 12 months after end of monalizumab treatment), unless disease progression (International Workshop on Chronic Lymphocytic Leukemia (IWCLL)), untoward toxicity, or consent withdrawal leads to the premature interruption of the ibrutinib treatment.

[figure not shown]
Page 8 of 26

TPL N°: eTPL SA-02-01 Of SOP SA-02.08 TPL Effective Date: 31 Mar 2016 TPL Version: 02
Approved in Vault: 3/8/2019

Patients will be enrolled for a post study follow-up enabling the investigator to document disease progression (IWCLL) or death, for 3 additional years after the completion of their in study follow-up.

The following figure illustrates the treatment schedule in both phases:

EOT: End of Treatment; EOS: End of Study

TPL Effective Date: 31 Mar 2016 Approved in Vault: 3/8/2019

The schedule of assessments is shown in Table 1 and Table 2.

Table 1

PHASE I Flow-chart	Screening ³	W0 C1	W0D2 C1	W0D8 C1	W2 C2	W2D2 C2	W4 C3	W4D2 C3	W4D8 C3	W6 C4	W6D2	W8 to W52 C5 to C16	EOT ⁹ W56	FU1 to FU7 ¹⁵	EOS ¹²
Informed consent	X												- 8	8	A S
Inclusion / Exclusion criteria	X	X											- 3		36
Demography, Medical history	X							370.00							
Concomitant illness	X	X	X	X	X	X	X	X	X	X	X	X	X	X	X
Concomitant medication	X	X	Х	X	X	X	Х	Х	X	Х	Х	X	X	X	Х
Tumor assessment ¹⁴	X						X		- 3			X	X	X	X
IPH2201 administration		Х			Х		Х		001-0	X		X			
Ibrutinib administration ²							х	X	X.	Х	х	Х	Х	X	
Safety assessments													3		
Weight	X	X			X		X			X		X	X	X	X
Height	X														
Physical examination ⁴	X	X			X		X			X		X	X	X	X
Vital signs	X	X	X	X	X	X	X	X	Х	X	X	X	X	X	X
ECOG status	X	X			X		X			X	100	. X	X	X	X
Adverse events	-330	X	X	Х	X	X	X	X	X	X	X	X	X	X	X
12-lead ECG ¹¹	X	X	9 9	1					3	X		W16, W32	3		X
Laboratory assessments															
Hematology ⁵	X	X	Х	X	X	X	X	Х	X	X	X	X	X	X	X
Biochemistry ⁶	x	X	х	х	х	×	х	x	х	x	x	W8, W16, W24, W32 W40,W48	×	FU3, FU5, FU6, FU7	×
Coagulation factors ⁸	X						X					W8	X		
Thyroid gland'	X		8 8						- 3			1	3	ě.	X
Urinalysis ¹⁰	X						X					W32	X		s = 5001
Pregnancy test	1,000	X													X
HIV / HBV / HCV screen	X		18 8							- 1		3	- 8	5	8.8
Beta 2 microglobulin	X		10 3										- 3		9
Serum Ig ¹³	X											W16, W32	X		

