8.2 Rate of overall and partial remission

The rate of overall and partial remission is assessed 52 weeks after the initiation of combined treatment and during the in-study follow-up.

The rates of overall (i.e cCR, uCR or PR) and partial remission (PR) will be calculated in the main endpoint population (see §4.2.2). Within this population, the overall/partial remission rates will be computed as the number of patients with a any/partial remission at W52 divided by the total number of patients in the main endpoint population.

The rate of overall (and partial) remission will be summarized overall and by dose level and the 95% confidence interval for this rate will be calculated only overall and in the subgroup treated at the RP2D.

The Best Overall Response (BOR) of each patient will be displayed in a summary table. The BOR is the best response (i.e cCR, uCR, PR, SD, PD or NE) taking into account all assessment results until the last disease assessment. The PR does not need to be confirmed and there is no minimum duration for SD. However, a listing with all the derived BOR will be sent to the Sponsor for medical review before the database lock.

Page 18 of 26

TPL N°: eTPL SA-02-01 Of SOP SA-02.08 TPL Effective Date: 31 Mar 2016 TPL Version: 02
Approved in Vault: 3/8/2019

The evolution of tumor response over time will be displayed, separately by patient, via a Swimmer plot (an example of swimmer plot can be found on page 2 of the following document:

Version: 2.0

https://www.pharmasug.org/proceedings/2014/DG/PharmaSUG-2014-DG07.pdf).

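### SAP 8.2 lets best overall response run past progression and new anti-CLL therapy, and pools follow-up responses on ibrutinib alone with those seen by week 52 (minor)

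*SAP*

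**What the plan says.** SAP 8.2 ranks each patient's results (confirmed or unconfirmed complete remission, partial remission, stable disease, progressive disease, not evaluable) and takes the best, "taking into account all assessment results until the last disease assessment". A partial remission needs no confirmation. The only check named is a sponsor medical review of the derived values before database lock, and no criterion is given for it. I found no rule on progression or new anti-CLL therapy for response in SAP 8.1, in the rest of 8.2, or in the missing-data section (4.6).

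The parts of the plan that decide what can fall inside that window are:

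- **Ibrutinib after IPH2201.** SAP 3.2.3 continues ibrutinib "until the end of the study follow-up period (up to 12 months after end of monalizumab treatment"), and the protocol synopsis agrees. If IPH2201 stops early, Protocol 3.3.1 says that "the continuation of ibrutinib treatment is left to investigator's discretion".
- **Assessment in follow-up.** Protocol 6.4: "a tumor assessment by physical examination is required at all follow-up visits". Protocol 6.5 requires a tumour assessment at the End of Study visit as well.
- **Other anti-tumour therapy.** Protocol 5.3.2: "The following concomitant treatments are not permitted until the end of the treatment period (End of Treatment"). Protocol 6.3 holds that visit when treatment stops prematurely.
- **Withdrawn patients.** Protocol 4.3 says that "appropriate alternative treatment will be proposed by the investigator to the withdrawn patient".

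**The concern.** The trial asks what IPH2201 plus ibrutinib achieves. A best-response rule with no end other than the last assessment lets two other things into the answer.

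The first is response to a different treatment. A patient recorded as stable or progressing, who then starts other therapy and is assessed again, takes the later and better category.

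The second is response that first appears on ibrutinib alone. The protocol's own background says that complete responses on ibrutinib accumulate slowly over years. A BOR table that runs through a further year of ibrutinib will therefore look better than one closed at week 52, even if IPH2201 adds nothing, and the table as planned does not show which responses came when.

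This matters because BOR is the only tabulated response summary that reaches into follow-up. SAP 8.2 opens by saying that remission is also assessed during follow-up, and SAP 3.1.2.2 lists follow-up complete response as a secondary endpoint. Yet every rate formula in 8.1 and 8.2 is fixed at week 52.

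**Working it through.** **1. The plan's own figure.** SAP 3.3.2 gives 27 patients, success at 4 or more complete responses, null rate 0.05, alternative 0.20, one-sided alpha 0.05 and power 0.80. Exact binomial:

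- P(X ≥ 4 | n = 27, p = 0.05) = 0.0437
- P(X ≥ 4 | n = 27, p = 0.20) = 0.818

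The design reproduces. Nothing in this point changes it, and BOR has no stated figure of its own.

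**2. Can a response to other therapy enter BOR?**

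- When IPH2201 stops early, the End of Treatment visit is held, and the ban on other anti-tumour therapy ends there (Protocol 5.3.2, 6.3).
- Protocol 3.4 follows patients for 12 months after IPH2201 stops, and 9.1.2 continues observation to the end of study after early discontinuation.
- A patient withdrawn for progression is followed for at least 4 weeks, or until toxicity recovers or stabilises, and then has an End of Study visit with a tumour assessment (4.3, 6.5). Nothing bars other therapy in between.
- SAP 8.2 does not stop at progression, and one unconfirmed partial remission is enough.

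The route is open. It is limited by SAP 4.2.2, which removes patients who stopped IPH2201 for progression within 8 weeks from the population used for response. Each patient who enters this way adds 1/27 = 3.7 percentage points to a 27-patient table. The documents give no basis for estimating how many would.

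**3. How much could ibrutinib alone add?** Inputs from Protocol 1.1.5.1: complete response 6% at 12 months and 23% at 42 months in untreated patients; 3% and 7% in previously treated patients. The last pair is printed as a cumulative incidence of relapses; reading it as complete response is an assumption. In both parts, 52 weeks of combined treatment plus 12 months of follow-up is about 24 months on ibrutinib. Linear interpolation, also an assumption:

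- Untreated: 6 + (23 − 6) × (24 − 12)/(42 − 12) = 6 + 17 × 0.4 = 12.8%
- Previously treated: 3 + (7 − 3) × 0.4 = 4.6%

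| Population | 12 months | 24 months | Expected in 27 |
|---|---|---|---|
| Untreated | 6.0% | 12.8% | 1.6 → 3.5 |
| Previously treated | 3.0% | 4.6% | 0.8 → 1.2 |
| 50:50 mix | 4.5% | 8.7% | 1.2 → 2.3 |

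A rough check on the straight line: the same section gives a median time to complete response of 21 months in untreated patients. If half of the 42-month responses had come by then, the rate at 21 months would be 23/2 = 11.5%. The line gives 6 + 17 × 9/30 = 11.1%.

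**4. Which outputs move?** The complete remission rate (8.1) and the overall and partial rates (8.2) count status at week 52, so responses first seen later do not enter them. That leaves the BOR table, and the swimmer plot unless it marks changes of treatment.

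**The case against.** BOR is not a listed endpoint, and no test or decision rule refers to it. Ibrutinib is protocol treatment to the end of follow-up. Follow-up complete response is a declared phase IIa secondary endpoint. Protocol 7.1 even times the complete-response criteria at least 2 months after IPH2201 stops. On that reading, counting responses after IPH2201 follows the protocol, and separating the two drugs is a limit of any single-arm combination trial. This stands. It rules out a BOR cut at the end of IPH2201. A listing keyed to the last IPH2201 dose would also separate little, because phase IIa dosing ends at week 48 and the End of Treatment visit is at week 52.

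A reader might take the sentence in Protocol 4.3 on alternative treatment as showing that response is still assessed on new therapy. It does not: its paragraph opens after the End of Study visit and concerns survival information. Patients with unresolved toxicity are taken off study (3.3.1). For those who leave for safety, 3.5.1 promises progression and survival data, not response. The new-therapy route is therefore narrow. It is not closed, for the reasons in step 2 of the working.

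The individual listings, the swimmer plot and the sponsor's review would let a careful reader spot such cases. None of them states a rule, and the trial is open label.

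**Conclusion.** The gap is real and minor. As written, BOR can credit a response to other therapy and let it override progression, and it does not separate responses first seen after week 52. The first is possible but of unknown frequency. The second follows directly from the design and is partly intended, so the fault lies in the presentation and not in counting those responses.

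The size of the second effect depends on case mix, which the documents do not fix. On the assumptions shown, the complete-response rate without any IPH2201 effect roughly doubles between 12 and 24 months in untreated patients, and rises by 1.6 points in previously treated ones.

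A reader might infer that the primary result is inflated. The documents do not support that. The primary rate is exposed only if a patient stops IPH2201 early, starts other therapy and has a complete response confirmed by scan and marrow that counts at week 52. That combination is remote.

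A reader might also connect this to Protocol 10.2, which counts 4 or more complete responses by the end of the study. That differs from the week-52 rate in SAP 8.1, but it is a separate inconsistency and does not run through BOR.

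**What to change.** In SAP 8.2, replace the BOR window with:

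> BOR uses assessments up to the earlier of documented progression (that assessment included) and the start of any non-protocol anti-CLL therapy. BOR is tabulated (a) using assessments up to the W52 visit and (b) through EOS, with responses first documented after W52 shown separately.

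In SAP 8.1, add:

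> A CR first documented after the start of non-protocol anti-CLL therapy counts as a non-response, and the patient stays in the denominator.

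The split in (a) and (b) should use the same 52-week assessment as 8.1. In phase Ib the combination starts at week 4, so the visit meant should be named. The split will not isolate patients who stop IPH2201 early and stay on ibrutinib before week 52; the individual listings remain the place to see them.

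The cost is a few lines of SAP text and one derived flag from concomitant-medication data already collected to the End of Study visit. No visit, patient or sample-size figure changes. The BOR figures may come out slightly less favourable.

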8.3 Quantitative changes of the CLL clone in the peripheral blood

The median change from baseline value of the percentage of CLL cells of all lymphocytes and of the percentage of CLL cells of all Leukocytes will be displayed graphically for all patients.

8.4 Remission with undetectable MRD

Undetectable MRD is defined as the percentage of CLL cells of all lymphocytes below 0.01%. The rate of patients in cCR at W52 with undetectable MRD in peripheral blood and bone marrow will be summarized overall and by dose level, and the 95% confidence interval for this rate will be calculated only overall for the patients in the phase Ib and for the patients in the phase IIa. Remission with undetectable MRD needs to be confirmed, i.e. CR and undetectable MRD should be met jointly and confirmed jointly. The rate of remission with undetectable MRD in peripheral blood and in bone marrow will be displayed separately.

8.5 Duration of Remission (DOR), Duration of Complete Remission (DOCR), Progression free Survival (PFS) and Overall Survival (OS)

The duration of Remission (DOR) and duration of complete Remission (DOCR) will be assessed in the main endpoint population, whereas the Progression Free Survival (PFS) and Overall Survival (OS) will be assessed in the ITT/safety population.

The DOR, for the remission assessed at 52 weeks, is defined as the time from the date of first evaluation of the remission (CR or PR) to the first documentation of progressive disease, relapsed disease or death. In case an assessment of a progressive disease, relapsed disease or death record does not exist, the duration of remission is censored at the time of the last disease assessment date. The duration of remission is only calculated for the patients with a cCR, an uCR or a PR assessed at 52 weeks.

The DOCR is calculated similarly for the patients with a cCR assessed at 52 weeks.

The PFS is defined as the time from first dose administration until the occurrence of progressive disease, relapsed disease or death from any cause. Patients without an event at the time of the analysis will be censored at his or her last disease assessment date; patient with no post-baseline assessments will be censored at the day of first dose administration.

The OS is defined as the time from first dose administration until death from any cause. Alive Patients are censored at the most recent date they are known to be alive. Subjects with no assessment post-baseline will be censored at the day of first dose administration.

The Kaplan-Meier method will be used to display graphically the DOR, PFS and OS for all patients. The number of patients and the number of DOR, PFS and OS events will also be displayed on the graph. The median (with its 95% confidence interval) DOR and DCOR will be displayed. Listing with individual values will also be displayed.

Page 19 of 26

TPL N°: eTPL SA-02-01

TPL Version: 02

Of SOP SA-02.08 TPL Effective Date: 31 Mar 2016

[figure not shown]

9. Safety Evaluation

All safety analyses will be done for the ITT/safety population.

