- 14 Tumor Assessment: pretreatment tumor assessment should be performed within 3 weeks before the first dose. Tumor assessments by physical examination should be performed at W4, W8; afterwards at all visits until EOS. A CT scan (with contrast unless contraindicated) of the chest, abdomen, and pelvis is required for the pretreatment tumor assessment. New CT-scan should be performed at W4, and thereafter at W16 and at EOS, and to confirm any CR or progression.
- 15 Follow up visits: to be performed every 3 months after EOT and during 12 months
- 16
  17 For patients in Phase 2a part, PK assessments at W0 H0 (pre-dose) and H0+1 (end of IPH2201 infusion); W0D1, W6, W12, W20, W28, W36, W44, W52 at H0 and H0+1; EOT, FU1 to FU4 (every 3 months); EOS

A bone marrow examination is required at screening if not performed within 1 month; at least 2 months after the achievement of complete response (CR) criteria clinically and in peripheral blood, in order to confirm the CR; and in the event of disease progression.

Release date: Edition number

MOD-3783

12 August 2016

GED version

Correlation tables of visit names between Protocol V4.0 and Protocol V5.0 for patients enrolled according to previous versions of protocol

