# 3.5 DISCONTINUATION

### 3.5.1 Discontinuation of the individual treatment

If a patient is progressing at any time during the study, treatment administration will be discontinued and the patient will be withdrawn from the study. For patient withdrawal, see section 5.3.

If a patient discontinues the study for safety reason, disease progression and survival information will be collected.

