4.2.2 Main endpoint population

The main endpoint population will include all patients:

Page 14 of 26

TPL N°: eTPL SA-02-01 Of SOP SA-02.08 TPL Effective Date: 31 Mar 2016 TPL Version: 02

Approved in Vault: 3/8/2019

- who have received at least one dose of monalizumab.
- who have received their first dose (W0D1) at least 52 weeks before the data cutoff date.

Patients who discontinued from monalizumab treatment due to disease progression before the end of 8 weeks of treatment will not be part of this population.

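### Duration of remission runs from first response but is computed only for patients still in remission at week 52, so responders who fail earlier drop out and the estimate is biased upward

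*SAP*

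**What the plan says.** SAP 8.5 gives DOR a time origin at first response: it is "defined as the time from the date of first evaluation of the remission (CR or PR"), and it ends at progression, relapse or death. The same section then limits who is analysed: "The duration of remission is only calculated for the patients with a cCR, an uCR or a PR assessed at 52 weeks". For complete remission, "The DOCR is calculated similarly for the patients with a cCR assessed at 52 weeks". SAP 8.2 computes the response rates from status at W52, so the 52-week condition means being in remission at that visit, not having been in remission at some time before it.

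The planned outputs are a Kaplan-Meier curve for DOR and, for both durations, a median: "The median (with its 95% confidence interval) DOR and DCOR will be displayed".

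Three other provisions bear on this:

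- Response is assessed early and often. The phase II flow-chart footnotes in the Protocol state: "Tumor assessments by physical examination should be performed at W4, W8; afterwards at all visits until EOS".
- Under Protocol 3.5.1, when a patient progresses, "treatment administration will be discontinued and the patient will be withdrawn from the study".
- SAP 8.2 looks beyond week 52: "The rate of overall and partial remission is assessed 52 weeks after the initiation of combined treatment and during the in-study follow-up".

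The Protocol (3.1.2) lists duration of response as a secondary endpoint with no week-52 condition.

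**The concern.** The clock starts at one time and eligibility is decided later, by the outcome being measured. A responder who progresses or dies before week 52 has a complete, observed DOR but is excluded. A responder who is included carries event-free time from first response to week 52 that the selection rule guarantees. This is immortal-time bias. Neither document plans a landmark origin, delayed entry or an all-responder analysis to correct it.

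At stake are the DOR curve and the DOR and DOCR medians with their confidence intervals. They would be read as how long responses last, but they describe only responses that had already lasted to week 52.

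A second gap has no known direction: a remission first reached after week 52 gets no duration. This matters mainly for DOCR. Protocol 1.1.5.1 reports, for ibrutinib alone in untreated patients, CR in 6% at 12 months and 23% at 42 months, with a median time to CR of 21 months. CRs after week 52 are therefore likely.

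**Working it through.** The documents state no DOR figure to reproduce. The phase IIa size of 27, used below for scale, does reproduce: with success at 4 or more CRs, the exact binomial gives one-sided alpha 0.0437 at p = 0.05 and power 0.8177 at p = 0.20.

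**Inputs**
- Loss rate: ibrutinib-alone PFS of 75% at 26 months (Protocol 1.1.5.1), taken as exponential, S(t) = 0.75^(t/26). This is a proxy. It covers all treated relapsed or refractory patients and may overstate loss among responders.
- Response rate: 71% (relapsed/refractory) to 86% (untreated), same section.
- Time of first response: not given, so assumed and varied.
- 4.348 weeks per month.

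**Formulas**, for first response at week w
- Guaranteed event-free time: g = (52 − w)/4.348 months.
- Share of responders excluded: 1 − S(g).
- True 12-month remission: S(12) = 0.75^(12/26) = 87.6%.
- Apparent 12-month remission under the SAP rule: S(12)/S(g), valid because every g is below 12 months.

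| First response | g (months) | Excluded | Apparent 12-month remission (true 87.6%) |
|---|---|---|---|
| W4 | 11.04 | 11.5% | 98.9% |
| W8 | 10.12 | 10.6% | 97.9% |
| W16 | 8.28 | 8.8% | 96.0% |
| W28 | 5.52 | 5.9% | 93.1% |
| W48 | 0.92 | 1.0% | 88.5% |

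For a mix of response times with equal weight every 4 weeks, the exclusion is 1 − mean S(g) and the apparent value is S(12)/mean S(g):

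| First responses spread over | Excluded | Apparent 12-month remission |
|---|---|---|
| W4–W28 | 8.7% | 95.9% |
| W4–W48 | 6.3% | 93.5% |
| W16–W52 | 4.4% | 91.6% |

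**In patients.** Responders number 27 × 0.71 = 19.2 to 27 × 0.86 = 23.2. Exclusions run from 19.2 × 0.059 = 1.1 (all first responses at W28) to 23.2 × 0.115 = 2.7 (all at W4). For the W16–W52 spread they are 19.2 × 0.044 to 23.2 × 0.044, about 0.8 to 1.0.

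**In events.** A simulation of 200,000 responders at this loss rate (first response evenly over W4–W40 visits, censoring at W104) dropped 7% of responders but 39% of DOR events. Kaplan-Meier 12-month remission was 94.5% under the SAP rule and 87.6% for all responders.

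**Median.** At this loss rate the true median is 26 × ln 0.5/ln 0.75 = 62.6 months. About 60 months of observation are planned (12 on treatment, 12 in-study, 36 post-study) and S(60) = 0.515, so the median may not be reached and the bias would show in the curve. If the true median were 24 months, a purely hypothetical value, the selected median would be 24 + g: 35.0 months for W4 and 29.5 for W28.

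**Phase Ib.** The 52 weeks run from the start of the combination, about W56 from first dose, which adds about 4 weeks to each gap counted from first dose.

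**The case against.** The strongest reply is about size. PR normally needs a fall in lymphocytes, which this drug class delays through redistribution lymphocytosis. PR with lymphocytosis is not among the categories listed in SAP 8.5. Routine on-treatment CT falls only at W4 and W16, and in phase Ib W4 precedes any ibrutinib. Very early first responses are thus unlikely to be the rule, and the W4 row is an extreme. A response first seen at W52 has no guaranteed time at all. This stands: the W16–W52 spread brings the effect down to about one patient and 4 percentage points. It does not change the direction.

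It is also true that no 12-month estimate is a planned output (it serves here to measure how far the curve shifts), that the 24-month median has no basis in the documents, and that no size has been computed for DOCR. CRs present at week 52 may be few and recent, so the guaranteed time there may be short.

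Other outputs partly mitigate: PFS is analysed in ITT/safety, and best overall response and the swimmer plot use all assessments, so early relapses remain visible. None of these corrects the DOR curve or median. SAP 8.5 does say the curve is for all patients, but that does not lift its explicit restriction.

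**Conclusion.** The concern holds. As written, SAP 8.5 excludes responders who progress or die before week 52 and credits the rest with guaranteed event-free time, so this mechanism biases DOR upward whenever any responder fails before week 52; if none does, the bias is nil.

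On the protocol's own ibrutinib PFS as a proxy, about 1 to 3 responders would be lost. The spreads examined move 12-month remission from 87.6% to between 91.6% and 95.9%. These figures rest on exponential loss and assumed response times. The omission of remissions first reached after week 52 is a separate gap of unknown direction.

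DOR is secondary and descriptive, and no decision rule uses it. The change should be made, but it does not threaten the trial's main conclusion.

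**What to change.** In SAP 8.5:

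1. Calculate DOR for every patient with PR or better at any time, from first response to progression, relapse or death, censored at the last disease assessment. Calculate DOCR for every patient with a confirmed CR at any time.
2. Use the ITT/safety population for both. Section 8 already assigns the 8.5 endpoints to it, whereas 8.5 names the main endpoint population for DOR and DOCR. In that population, patients who stopped monalizumab "due to disease progression before the end of 8 weeks of treatment will not be part of this population". Few of those would be prior responders, so this change mainly removes a contradiction.
3. If an analysis of week-52 responders is kept, start its clock at week 52 and label it a landmark analysis.

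The cost is SAP wording and programming, with no new data. The reported DOR may be shorter.
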